TITLE	A Phase I/II Trial Of Temozolomide And Hypofractionated Radiotherapy In The Treatment Of Supratentorial Glioblastoma Multiforme
STUDY PHASE	I/II
INDICATION	Newly diagnosed, histologically confirmed supratentorial GBM.
PRIMARY OBJECTIVES	Phase I - Primary Objective Determine the maximum tolerated dose (MTD) of hypofractionated radiotherapy given in 5 fractions with temozolomide for the treatment of glioblastoma multiforme.
SECONDARY OBJECTIVES	Determine the short- and long-term adverse effects. Determine the radiographic response rate. Determine the overall survival rate. Perform patterns of failure analysis. Assess quality of life during treatment.
HYPOTHESES	Five fraction stereotactic radiosurgery (SRS) with concurrent temozolomide will be well-tolerated; the duration of radiotherapy can safely be shortened to 5 treatments without compromising the local control or overall survival rates.
STUDY DESIGN	Phase I: The MTD for five-fraction SRS concurrent with temozolomide will be determined using a 3+3 study design.
PRIMARY ENDPOINTS AND SECONDARY ENDPOINTS	Phase I Primary endpoint The MTD and DLT of hypofractionated radiotherapy with temozolomide will be determined. Secondary endpoints The short- and long-term adverse effects will be determined. The overall survival rate will be calculated. Patterns of failure analysis will be performed. Health related quality of life will be measured.
SAMPLE SIZE BY TREATMENT GROUP	Three patients will be enrolled per dose level per arm. The maximum number of patients

	needed for the phase I study will depend on the number of dose levels reached. If all 4 dose levels are reached, the maximum number of patients will be 15 per arm.
SUMMARY OF SUBJECT ELIGIBILITY CRITERIA	
Inclusion Criteria
 
 • Histopathologically confirmed newly diagnosed glioblastoma multiforme. Diagnosis must be made by surgical biopsy or excision. • The tumor must be supratentorial in location. • The planning target volume (tumor plus margin) must measure $\leq 150 \text{ cm}^3$ in volume. • Age ≥ 18 years. • Life expectancy of at least 12 weeks. • Patient must have adequate organ function to tolerate temozolomide (details in the protocol). 
Exclusion Criteria
 
 • Patients who have previously been treated with brain irradiation to the region that would result in overlap of the radiation fields. • Tumor foci detected below the tentorium. • Multifocal disease or leptomeningeal spread. • Prior allergic reaction to the study drugs involved in this protocol. • Inability to have neither an MRI nor a CT scan. Patients with pacemaker will be allowed to undergo CT instead of MRI. • Pediatric patients (age < 18), pregnant women, and nursing patients will be excluded.
INVESTIGATIONAL PRODUCTS DOSAGE AND ADMINISTRATION	N/A
CONTROL GROUP	N/A
PROCEDURES	N/A
STATISTICAL CONSIDERATIONS	N/A

SCHEMA

Phase I:

PTV (Planning Target Volume) is defined as the residual T1 post-contrast enhancing tumor and/or resection cavity + 0.5 cm margin (see Section 4.3.4).

Patient Population: (See Section 3.0 for Eligibility)

Histopathologically confirmed supratentorial glioblastoma multiforme without previous radiation to the same region.

LIST OF ABBREVIATIONS

AE	Adverse Event
ANC	Absolute neutrophil count
CBC	Complete blood count
CNS	Central nervous system
CR	Complete response
CRF	Case report/Record form
CTCAE	Common Terminology Criteria for Adverse Events
CTV	Clinical Tumor Volume
DLT	Dose Limiting Toxicity
DSMB	Data Safety Monitoring Board
EORTC	European Organisation for Research and Treatment of Cancer
GBM	Glioblastoma multiforme
GI	Gastrointestinal
GTV	Gross Tumor Volume
Hgb	Hemoglobin
HRQOL	Health Related Quality of Life
IRB	Institutional Review Board
IV	Intravenous
LLN	Lower limit of normal
MR	Minor response
MTD	Maximum tolerated dose
OS	Overall survival
P	Progressive diseased
PFS	Progression free survival
PLT	Platelet
PR	Partial response
PTV	Planning Target Volume
QD	Once daily
RT	Radiotherapy
SAE	Serious adverse event
SD	Stable disease
SRS	Stereotactic Radiosurgery
STEAE	Serious treatment emergency adverse event
TMZ	Temozolomide

1. OBJECTIVES

1.1.Phase I - Primary Objective

- 1.1.1 Determine the maximum tolerated dose (MTD), based on acute CNS toxicity at 30 days, of hypofractionated radiotherapy given in 5 fractions with temozolomide for the treatment of glioblastoma multiforme.

1.2.Secondary Objectives

- 1.2.1. Assess the short- and long-term adverse effects.
- 1.2.2. Determine the radiographic response rate.
- 1.2.3. Determine the overall survival rate.
- 1.2.4. Determine the patterns of tumor failure.
- 1.2.5. Assess quality of life during treatment.

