1.2. Hypofractionated Radiotherapy

Standard therapy for GBM includes 6 weeks of daily radiation treatments. This treatment course can pose a substantial hardship for patients and their families, particularly for those living distant from a radiation facility. Despite aggressive multimodality treatment, the median survival is only 14 months(4).

Compared to standard fractionation, hypofractionated radiotherapy or stereotactic radiosurgery (SRS) delivers higher doses of radiation in fewer treatment sessions (5 treatments versus 30 for conventionally fractionated RT). SRS for GBM has several potential advantages: First, SRS drastically reduces the total treatment time thereby potentially maximizing the patients' quality of life. A five week decrease in treatment time represents approximately 10% of the median lifespan of these patients. Similarly, this goal on the use of SRS to shorten the treatment time for an otherwise incurable tumor

has been studied and achieved for pancreas cancer(5-7). A similar shortening of treatment time has been investigated in breast cancer, where the standard 33 days of therapy have been replaced with a single day(8). Second, by shortening the treatment duration, hypofractionation may lead to suppression of tumor cell repopulation and improve tumor control. An *in vitro* study of glioblastoma cell lines have demonstrated repopulation of glioblastoma cells during fractionated radiotherapy, thereby requiring higher radiation dose to achieve cell kill(9). Likewise, longer treatment duration has been shown to decrease local control in multiple other tumor types(10). Third, GBM may show improved response to higher radiation doses per fraction. Hypofractionated radiotherapy has been shown to cause improved tumor regression in mouse xenografts compared to conventional or hyperfractionated radiotherapy(11). Moreover, GBM tumors carrying a p53 mutation are more resistant to conventionally fractionated radiotherapy, and improved cell kill has been demonstrated with hypofractionation(12).

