4.3 Radiation Therapy

1.1.1. Dose specifications/escalation

Radiation will be delivered in five fractions. Provided that the MTD has not been reached, the total dose will be increased as follows:

Dose Level	Dose Per Fraction (Gy)	Total Dose (Gy)
1	5	25
2	6	30
3	7	35
4	8	40

There will be 2 arms to this study:

Arm	PTV volume (cm ³)
1	< 60
2	60-150

A minimum observation period of 30 days following radiotherapy is required prior to proceeding with the next higher dose level.

Common Terminology Criteria for Adverse Events (CTCAE) v4.0 will be used to grade adverse events:

(<http://evs.nci.nih.gov/ftp1/CTCAE/About.html>)

A dose limiting toxicity (DLT) is defined as a treatment related grade 3 - 5 CNS toxicity. Acute toxicity is defined as occurring within <30 days of the end of

radiotherapy. Late toxicity is defined as occurring ≥ 30 days of the end of radiotherapy. The highest dose achieved with an acceptable level of toxicity will be considered the MTD. The highest dose level allowed in this study is 40 Gy. The occurrence of late toxicities will be continuously monitored. If a late DLT occurs in 2 patients at a certain dose level after the radiation dose had already been escalated to the next level, the MTD will be backtracked to the level below the one at which the DLTs occurred.

Dose escalation will follow a traditional 3 + 3 design:

Number of Patients with DLT at a Given Dose Level	Escalation Decision Rule
0 out of 3	Enter 3 patients at the next dose level.
1 out of 3	Enter at least 3 more patients at the current dose level. 
 • If 0 of these 3 experiences a DLT (i.e., 1 out of 6), then proceed to next dose level. • If 1 or more of these 6 experiences a DLT (2 or more out of 6), then dose escalation will be stopped. Three additional patients will be entered at the next lower dose level if only 3 patients were previously entered.
>1 out of 3	Dose escalation will be stopped. Three additional patients will be entered at the next lower dose level if only 3 patients were previously entered.

Should a patient not be evaluable at 30 days (due to death unrelated to protocol treatment or loss to follow-up or discontinuation of the protocol follow-up per patient preference), then additional patients may be enrolled on each arm such that at least 3 are evaluable for DLT.

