1.2.7. Dose definition and administration

Oral temozolomide (75 mg/m²/day) will be administered daily during radiotherapy. The first dose of temozolomide will begin the day before the first fraction of radiation. The last dose will be taken the day of the last fraction of radiation. Following radiotherapy, maintenance temozolomide will be prescribed at the discretion of the treating neuro-oncologist.

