8. STUDY CALENDAR

Parameters	Pre-Entry	1 month ^a	6 month ^e	12 month ^e
History/ Physical Exam	X	X	X	X
KPS	X	X	X	X
HRQOL ^b	X	X	X	X
Labs ^c	X			
Brain MRI or CT ^d	X	X	X	X
Steroid use Assessment	X	X	X	X
Toxicity Evaluation		X	X	X
	^a ± 7 days			

	
^b EORTC-QLQ C30 and BN-20, MDASI-BT
 
^c Laboratory tests: complete blood count, general chemistry panel, and comprehensive metabolic panel
 
^d MRI schedule may change as indicated should patient have clinical deterioration; CT instead of MRI is acceptable if patient has pacemaker.
 
^e ± 1 month

--	---

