9.2 Other Response Parameters

9.2.1 Acute and late side effects will be assessed.

Common Terminology Criteria for Adverse Events (CTCAE) v4.0 will be used to grade adverse events. Acute toxicity is defined as occurring within 30 days of radiotherapy. Late toxicity is defined as occurring more than 30 days following the radiotherapy treatment.

9.2.2 The progression-free survival rate will be determined.

9.2.3 The overall survival rate will be determined.

9.2.4 The patterns of tumor recurrence will be determined.

9.2.5 The Health Related Quality of Life (HRQOL) will be measured used the validated EORTC QLQ-C30 general and BN-20 brain tumor specific scales as well as the M.D. Anderson Symptom Inventory –Brain Tumor (MDASI-BT)

For those subjects unable to appear in person for clinic visits, HRQOL questionnaires will be completed via a telephone interview or mail.

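### Quality of life during treatment is a stated objective, but no HRQOL assessment is scheduled within the five-fraction course

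*Combined protocol and SAP*

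**What the plan says.** Objective 1.2.5 reads "Assess quality of life during treatment", and the synopsis repeats it among the secondary objectives.

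The course is short. Under dose specifications in section 4.3, "Radiation will be delivered in five fractions". For the drug, section 4.4 says "The first dose of temozolomide will begin the day before the first fraction of radiation" and "The last dose will be taken the day of the last fraction of radiation". Maintenance temozolomide after that is left to the treating neuro-oncologist. Section 5 gives no dose-modification rules because treatment is so short.

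The study calendar (section 8) marks HRQOL at pre-entry, 1 month (within 7 days either way), and 6 and 12 months (within 1 month either way). Its footnote lists the instruments as "EORTC-QLQ C30 and BN-20, MDASI-BT". Section 9.2.5 names the same instruments but no time points. It adds that, for patients who cannot attend clinic, "HRQOL questionnaires will be completed via a telephone interview or mail". The endpoint statement in section 11.1.2 says only that HRQOL is to be assessed, without tying it to treatment.

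**The concern.** The objective names a period in which the calendar collects nothing. If HRQOL worsens during the radiotherapy week and recovers before the 1-month visit, the trial will not see it. Section 6.1.1 expects early effects of the kind that would show on these questionnaires: fatigue, headache, nausea, vomiting and lethargy. The 1-month result might then be reported against objective 1.2.5 although it is a post-treatment value.

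What is at stake is modest: how one descriptive secondary objective is read. No hypothesis, power calculation or decision rule depends on HRQOL.

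**Working it through.** The plan states no HRQOL sample size, margin or power, so there is no such figure to reproduce. The check compares the treatment window with the assessment dates.

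**Inputs from the protocol**
- Treatment window: the day before fraction 1 to the day of the last fraction (section 4.4, repeated in section 4.6).
- Course length: five fractions; the spacing is not stated. Background section 1.2 gives standard therapy as 6 weeks and says "A five week decrease in treatment time represents approximately 10% of the median lifespan of these patients", which implies 6 − 5 = about 1 week.
- HRQOL dates: pre-entry, 1 month ± 7 days, 6 and 12 months ± 1 month (section 8).
- Anchor: sections 4.7 and 9.1 count the MRIs at these same time points from the end of treatment or radiotherapy. The calendar does not state an anchor for HRQOL.

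**Assumptions varied**
- Course length D = 5, 7, 9 or 14 days.
- Month length m = 28, 30 or 31 days.
- Visits counted from the last or from the first fraction.

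**Counted from the last fraction**
- Earliest gap = m − 7: 28 − 7 = 21, 30 − 7 = 23, 31 − 7 = 24 days.
- Latest gap for a 30-day month: 30 + 7 = 37 days.
- The 1-month questionnaire therefore falls on days 23 to 37 after the last fraction with a 30-day month.

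**Counted from the first fraction**
- The last fraction is D − 1 days after the first, so the earliest gap = m − 7 − (D − 1).
- Longest: m = 31, D = 5 gives 24 − 4 = 20 days.
- Shortest: m = 28, D = 14 gives 21 − 13 = 8 days.

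**Result.** In all 4 × 3 × 2 = 24 combinations the first post-baseline questionnaire falls after the last fraction. Pre-entry precedes treatment, and 6 and 12 months are later still. Assessments inside the course: 0 of 4.

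**Does anything else fill the gap?** The extra contacts in section 4.7 are clinical follow-up and MRI. The Appendix B follow-up form offers 1, 6 and 12 months or an unspecified other visit. It has a quality-of-life row, so an unscheduled questionnaire could be recorded, but none is called for during the course.

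**Patients affected by an added assessment**
- The protocol's maximum per arm (section 11.2.1): 4 levels × 3 + 3 at the MTD = 15, so 2 arms × 15 = 30.
- That is not the ceiling under the 3+3 rule. A level with 1 DLT in 3 expands to 6 and can still escalate, so 4 levels × 6 = 24 per arm and 48 in total, before replacement of non-evaluable patients.

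**The case against.** **Treatment may include maintenance temozolomide.** The last paragraph of the Background describes the regimen as having both concurrent and adjuvant temozolomide, and section 4.6, on duration of therapy, mentions maintenance. On that reading the 1-, 6- or 12-month questionnaires could be completed on treatment by some patients. This stands in part. A reader might infer from 0 of 4 that the trial can say nothing about the objective; the documents do not support that, because the word is ambiguous. But maintenance is discretionary, has no protocol schedule and is not linked to HRQOL visits. The follow-up form records dexamethasone but has no field for temozolomide, so it would not show which questionnaires were completed on treatment. Section 5 favours the narrow reading, and on either reading the radiotherapy course is unmeasured.

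**The rationale does not concern the radiotherapy week.** Background section 1.2 argues that "SRS drastically reduces the total treatment time" and may thereby improve quality of life. A reader might infer that the gap undermines this main rationale. It does not: the argument there is about fewer weeks spent in treatment, and with no control group an added questionnaire could not test it. The 1-month visit may even be the more relevant one. With a 5- to 7-day course and fraction 1 as day 1, it falls between day 5 + 23 = 28 and day 7 + 37 = 44, when a 42-day course would mostly still be running. This stands.

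**The endpoint wording already fits the calendar.** Section 11.1.2 and the synopsis endpoints omit *during treatment*, so deleting two words would remove the conflict. This stands, and is the fallback below.

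**One assessment on the last day cannot show recovery.** It also precedes most of the 30-day early-effects period. This stands and limits what the added assessment can deliver.

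**Conclusion.** The mismatch is real. None of the four scheduled HRQOL assessments falls within the five-fraction course with concurrent temozolomide, under any course length from 5 to 14 days, any month length of 28 to 31 days examined, and either anchor. With a 30-day month counted from the end of radiotherapy, the first post-baseline value comes 23 to 37 days after the last fraction. As scheduled, the data support change from before to after radiotherapy, not quality of life during the course.

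The conclusion assumes that treatment means the protocol-specified course. On the wider reading some information is available from patients who happen to be on maintenance, but it is unscheduled and not identifiable from the follow-up form. The documents state no recall period for the questionnaires; with a 30-day month counted from the end of radiotherapy, recall would have to reach back at least 23 days to touch the course.

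This is a small but worthwhile correction to a descriptive secondary objective. It does not affect the MTD, the DLT rules or the sample size.

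**What to change.** 1. Add one set of the questionnaires already in use on the day of the last fraction, when the patient is attending anyway, with a matching calendar column and form option. This gives an end-of-treatment value to set against pre-entry and 1 month. It will not trace the course of recovery between those two points, and the protocol should not claim that it does.
2. Reword objective 1.2.5 and the synopsis to match: change in HRQOL from pre-entry to the end of radiotherapy and to 1, 6 and 12 months.
3. If no assessment is added, delete *during treatment* from both places, state the objective as change from pre-entry to 1, 6 and 12 months, and make no claim about the treatment period.

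The cost of the first option is one extra questionnaire set per patient: 30 sets on the protocol's stated figure, up to 48 with full expansion in both arms, before replacements. The burden on each patient is small. The third option costs only a wording change.

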2. BACKGROUND

1.1. Glioblastoma Multiforme

High grade gliomas are the most common primary brain tumor. Glioblastoma multiforme (GBM) is characterized by its highly aggressive nature and poor prognosis. The annual incidence of GBM in the U.S. is 12,000 and rising. Multi-modality therapy with surgery, radiation (RT), and chemotherapy is the standard treatment for all patients whose performance status allows aggressive treatment. Even after a gross total resection, the local recurrence rate is high. Post-operative radiotherapy has been shown to increase local control and overall survival rates(1, 2). For elderly patients and patients with poor performance status, radiation therapy without chemotherapy provides palliation and prolongs survival(3).

1.2. Hypofractionated Radiotherapy

Standard therapy for GBM includes 6 weeks of daily radiation treatments. This treatment course can pose a substantial hardship for patients and their families, particularly for those living distant from a radiation facility. Despite aggressive multimodality treatment, the median survival is only 14 months(4).

Compared to standard fractionation, hypofractionated radiotherapy or stereotactic radiosurgery (SRS) delivers higher doses of radiation in fewer treatment sessions (5 treatments versus 30 for conventionally fractionated RT). SRS for GBM has several potential advantages: First, SRS drastically reduces the total treatment time thereby potentially maximizing the patients' quality of life. A five week decrease in treatment time represents approximately 10% of the median lifespan of these patients. Similarly, this goal on the use of SRS to shorten the treatment time for an otherwise incurable tumor

has been studied and achieved for pancreas cancer(5-7). A similar shortening of treatment time has been investigated in breast cancer, where the standard 33 days of therapy have been replaced with a single day(8). Second, by shortening the treatment duration, hypofractionation may lead to suppression of tumor cell repopulation and improve tumor control. An *in vitro* study of glioblastoma cell lines have demonstrated repopulation of glioblastoma cells during fractionated radiotherapy, thereby requiring higher radiation dose to achieve cell kill(9). Likewise, longer treatment duration has been shown to decrease local control in multiple other tumor types(10). Third, GBM may show improved response to higher radiation doses per fraction. Hypofractionated radiotherapy has been shown to cause improved tumor regression in mouse xenografts compared to conventional or hyperfractionated radiotherapy(11). Moreover, GBM tumors carrying a p53 mutation are more resistant to conventionally fractionated radiotherapy, and improved cell kill has been demonstrated with hypofractionation(12).

Several groups have employed hypofractionated radiotherapy alone, without chemotherapy, for treatment of high grade glioma and have shown hypofractionated RT to be well tolerated. Thomas has shown the regimen of 30 Gy in 5 Gy fractions was without acute toxicity(13). Floyd *et al.* delivered 50 Gy in 5 Gy fractions over a 2-week course. While 3 of 20 patients in this study underwent surgical re-excision due to radiation necrosis, these three patients also enjoyed longer survival (range, 9-23 months)(14). Hulshof compared conventional fractionation with hypofractionation using 66 Gy in 2 Gy (conventional fractionation), 40 Gy in 5 Gy, and 28 Gy in 7 Gy fractions. Patients treated with the conventional radiation schedule had similar median survival as the 28 Gy in 7 Gy fraction group despite having patients with significantly worse prognostic factors in the hypofractionation group(15). In a prospective trial of patients older than 60 years, a shorter course of radiotherapy, using 40 Gy in 15 fractions (2.67 Gy fractions) over 3 weeks, decreased treatment time and corticosteroid requirement without negatively affecting survival when compared to conventional radiotherapy (60 Gy in 2 Gy fractions over 6 weeks)(16).

A major concern of using high doses per fraction is the potential for neurotoxicity. Multiple studies have demonstrated doses ranging from 2.5 to 7 Gy per fraction to be well tolerated in patients without prior radiation(13, 17-19). Hypofractionated radiotherapy has also been shown to be safe in patients with prior radiation: In a study by Hudes and colleagues, patients with recurrent or persistent malignant glioma who had previously received a median dose of 60 Gy (range, 44 – 72 Gy) of external beam radiation were treated with stereotactic radiotherapy to target recurrent or persistent tumors in a phase I dose escalation study. Although there was no tumor response to 24 Gy in 3 Gy fractions, 79% responded to 30 Gy in 3 Gy or 35 Gy in 3.5 Gy fractions. There was no grade ≥ 3 toxicity, and no patient required a re-resection due to toxicity(20). Shepherd *et al.* reported hypofractionated stereotactic radiotherapy in treatment of recurrent glioma using 5 Gy fractions to total doses ranging from 20 to 50 Gy to be well tolerated, with 36% having reversible steroid-dependent toxicity and only 6% requiring reoperation(21).

